# D. Study Termination

The investigator with appropriate notification may terminate the study. If, after clinical observations, the investigator feels that it may be unwise to continue the study, he or she may stop the study.

# E. Study Completion

The study will be complete when 30 subjects have completed Visit 11 or have been terminated from the study.

# 7. Adverse Events

#### 7.1 Potential Risks

Possible adverse events from **Kybella(TM)** Injections include:

- Raised red areas at the treatment site(s)
- Bruising
- Itching
- Pain/tenderness
- Edema
- Headache
- Paresthesia
- Ulcerations
- Erythema
- Nausea
- Infection
- Induration
- Skin discoloration
- Foreign body granuloma
- Persistent discoloration
- Scarring
- Dysesthesia
- Post-inflammatory hyperpigmentation
- Numbness of treatment site

The potential risks associated with Triamcinolone acetate, a commercially available injectable, include:

- Nausea
- Bloating
- Appetite changes
- Stomach or side pain

- Headache
- Sleep problems (insomnia)
- Acne or other skin changes
- Slow-healing wounds
- Thinning hair
- Bruising or swelling
- Sweating
- Irregular menstrual periods

The potential risks associated with **0.1% lidocaine**, a commercially available injectable, include:

- drowsiness, dizziness;
- feeling hot or cold;
- numbness in places where the medicine is accidentally applied

# 7.2 Unknown/Unforeseeable Risks

In addition to the risks listed above, there may be some unknown or infrequent and unforeseeable risks associated with Triamcinolone and/or Kybella(TM) injections. Patients will be informed both verbally and in writing in a timely manner of any new information, findings or changes to the way the research will be performed that might influence their willingness to continue their participation in this study.

**Pregnancy/Fetal Risks:** The effects of Triamcinolone and/or Kybella(TM) injections have not been studied in pregnancy and therefore **may be hazardous.** 

If a patient thinks that you may be pregnant or have become pregnant during the study the patient is to inform the study doctor immediately. If a patient becomes pregnant or thinks they may be pregnant, they will be removed from the study and the study doctor will refer the patient to seek obstetric care and may request to track their pregnancy and will report the pregnancy to the IRB.

#### 8. RESPONSIBILITIES OF THE INVESTIGATOR

# 8.1 Adherence to the Study Protocol

The Investigator must ensure adherence to the procedures outlined in this Study Protocol. The procedures set out in this study protocol, pertaining to the conduct, evaluation, and documentation of this study, are designed to ensure that the Investigator abides by GCP as described in the ICH Guidelines Topic E6: "Guideline for Good Clinical Practice." Compliance with these regulations also constitutes compliance with the ethical principles described in the current revision of the Declaration of Helsinki. The study will also be carried out in keeping with local legal and regulatory requirements.

#### 8.2 Data Handling and Record Keeping

The Investigator must ensure that proper source documentation for all study activities are diligently maintained and securely kept. The Investigator will transfer all relevant data to the

Case Report Form as stipulated in this Study Protocol and his/her signature on the Case Report Form guarantees completeness and integrity of these data. The Investigator will maintain reliable study records and will store study supplies in a secure, locked location. In addition, the Investigator will ensure that all Case Report Forms will be maintained for a period of two years after the conclusion of the study.

#### 9. REGULATORY OBLIGATIONS

# 9.1 Institutional Review Board

The study protocol, informed consent forms (all versions), and any specific advertising will be submitted to and approved by Independent Investigational Review Board before the start of the study. A form must be signed by the chairman or designee of the IRB noting the approvals. This notification will be provided to Allergan.

## 9.2 Protocol

The Investigator signing the protocol signature page will act as the Principal Investigator at this site. Protocols will be noted as approved by the Investigator by placement of his signature on the Investigator's Signature Page. Copies of the IRB approved protocol and informed consents will be provided to Allergan.

#### 9.3 Informed Consent

An Informed Consent (IC) that includes all of the relevant elements currently required by FDA or state regulations will be provided to each prospective study patient at screening and before enrollment into the study. The type and method of study, any potential or possible hazards, and the patient's right to withdraw from the study at any time will be explained to the patients by the Investigator of designee. Once the Investigator is assured that an individual candidate understands the implications of participating in this study, the patient will be asked to give consent by signing and dating in the appropriate areas of the Informed Consent form. The Investigator or Designee will also sign and date the form. A copy of the IRB approved IC form will also be provided to Allergan.

# 9.4 Protocol and Informed Consent Changes

Changes to the protocol or Informed Consent form(s) will be implemented as amendments to the original document and approved by the IRB. The approvals will be processed in accordance with the established IRB procedures. Copies of all protocol and IC amendments/revisions, along with letters noting IRB approval, will be submitted to Allergan, as this may affect safety. Any addenda, amendment or revision that substantially alters the study design or increases potential risk to the patient requires the patient's consent to continue in the study.

# 9.5 Study Monitoring

All monitoring activities are the responsibility of the clinical site. Monitoring is for the purpose of confirming adherence to the protocol and to verify complete and accurate data collection. The site will be responsible for internal verification of data throughout the study.

#### 10. Confidentiality of Records

Information about the subject's health taken during this study may be used and given to others by the study coordinators, the medical staff, the respective study center and by the subject's doctors and their other health care providers (together, they are called "providers"). These providers may share health information about the subject with the study coordinator. The study coordinator and the providers may share that information with researchers participating in this Study laboratories conducting tests for this Study; a final study report will be shared with the U.S. Food and Drug Administration (FDA); Department of Health and Human Services (DHHS) agencies; Other U.S. and foreign government agencies that watch over quality, safety, and effectiveness of research.

# 11. Delegation of Investigator Responsibilities

The Investigator should ensure that all persons assisting with the trial are adequately informed about the protocol, any amendments to the protocol, the study treatments, and their trial-related duties and functions. The investigator should maintain a list of Co-Investigators and other appropriately qualified persons to whom he has delegated significant trial-related duties.

#### 12. Direct Access to Source Data/Documents

The Investigator must ensure that institutional regulations, the Informed Consent Form, and the HIPAA Authorization clearly permit study-related monitoring, audits, REB review, and regulatory inspections providing direct access to source data and documents.

# 13. Adverse Events and Reporting

Serious and/or Adverse Event and Reporting

A *serious adverse event* is any untoward medical occurrence, that, at any dose:

- Results in death;
- is life-threatening;
- requires in-subject hospitalization or prolongation of existing hospitalization;
- Results in persistent or significant disability/incapacity;
- is a congenital anomaly/birth defect; or
- is an important medical event.

An *unexpected adverse event* is any treatment-related adverse event, which is not identified in nature, severity, or frequency in current literature on the test product.

Any serious adverse event occurring in this study must be reported to the IRB within 24 hours of awareness of the event. Initial reports must be made by telephone, followed by the completion of a Serious Adverse Event Report and submission by facsimile.

Throughout the study, subjects will be monitored for signs and symptoms of adverse events. An *adverse event* is any pathological or unintended change in the structure, function or chemistry of the body that occurs during the study, irrespective of causality, including any illness, injury, toxicity, sensitivity, or sudden death. The condition must either not be present pre-study or must worsen in either intensity or frequency during the study.

All adverse events, including serious and treatment related or unexpected adverse events, must be recorded by the Investigator. In the event of an adverse event or serious adverse event, the physician will provide optimal patient care.

Subjects who have had a serious adverse event must be followed clinically until all parameters have either returned to normal or are otherwise explained. If death was the outcome of the event on the initial SAE Report, a Follow-up/Final Report, including autopsy report, when performed, must be completed.

#### 14. DATA ANALYSIS

A blinded investigator will grade the side effects on a scale of 0-4 to assess erythema, edema, tenderness, and erosion/ulceration at each follow-up visit and utilize the Clinician-Reported Submental Fat Rating Scale of 0-4 will be completed on Visit Days 1, 30, 60, 90 and 180.

The subject will evaluate the side effects of bruising, pain, swelling, tolerability, and interference in daily function on a scale of 0-4 at all follow-up visits and complete the Subject Satisfaction Rating Scale of 0-6 on Visit Day 180 (See Appendix B). The investigator will also evaluate the side effects of bruising, pain, swelling, tolerability, and interference in daily function on a scale of 0-4 at all follow up visits.

A p value of 0.05 or less will be considered significant.

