A previous study was performed using high doses of a corticosteroid. This double-blind, randomized study utilized triamcinolone acetonide (TMC), a corticosteroid compound, in conjunction with Kybella(TM) showed that the addition of TMC reduced the incidence of early edema and tenderness, but negatively impacted long term efficacy and produced cutaneous changes of steroid atrophy in 7 (47%) of the 15 patients treated with TMC [4]. In the study, 2.0 mL of 2 mg/cm2 of Kybella(TM) was mixed with 0.05 mL of 40 mg/mL of TMC, and was delivered in up to 50 injections spaced 1.0 cm apart at 0.25 mL/injection for a total dose of up to 100 mg of Kybella(TM). As the tolerability of Kybella(TM) remains a significant issue in patient care, perhaps lower concentrations of TMC would be effective in reducing side effects without compromising treatment efficacy and causing steroid atrophy.

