#### 2. Study Objective & Hypothesis

The primary objective of this study is to evaluate the efficacy, edema and pain associated with Kybella(TM) injections of the upper neck in the treatment of submental fat with low concentrations of triamcinolone acetonide plus low doses of lidocaine. An evaluator blinded to the study will grade the level of improvement of the submental fat. Safety will also be assessed.

The Working Hypothesis: The combination of Kybella(TM) and with very low dose triamcinolone acetonide is effective in the reduction of immediate edema associated with Kybella(TM) injections and does not adversely affect the previously demonstrated long term reduction of submental fat. Addition of 0.1% lidocaine will provide immediate pain relief for a better patient experience. As 1% lidocaine is already injected just prior to Kybella injection as per current treatment protocol, there is no anticipated effect from low dose 0.1% lidocaine other than anesthesia.

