# 3. Study Design

This is a two-site randomized, double-blind comparison trial of Kybella(TM) injections with or without triamcinolone acetate for the reduction of submental fat. 30 subjects will be enrolled into the trial (15 subjects per site). At each site, 5 will be randomized to receive Kybella(TM) injections alone whereas 10 will receive Kybella(TM) plus differing doses of triamcinolone acetate in the following way:

- 1. Group 1 (5 patients per site): Kybella(TM) alone: 2 mg/cm^2 of Kybella(TM) with **0.2 mL** of 1% lidocaine with no epinephrine plus 0.2cc saline to the non-TMC group to maintain equal concentrations in each injection so that the final Kybella concentration per vial will be 10mg/1.2mls or 1.6mg per 0.2 cc injection point will be delivered in up to 50 injections spaced 1.0 cm apart at 0.2 mL/injection for a total maximal dose of up to 100 mg of SDOC.
- 2. Group 2 (10 patients per site): Kybella(TM)+TMC at **1.0 mg/mL**: 2.0 mL of 2 mg/cm^2 of Kybella(TM) will be mixed with **0.2 mL of 10 mg/mL** of triamcinolone acetate, **0.2 mL of 1% lidocaine with no epinephrine** and then delivered in up to 50 injections spaced 1.0 cm apart at 0.2 mL/injection for a total dose of up to 100 mg of SDOC using a 30 gauge (or smaller) 0.5-inch needle. The final Kybella concentration per vial will be 10mg/1.2mls or 1.6mg per 0.2 cc injection point

The treatment area will be bounded superiorly by a line 1 cm inferior to the mandibular margin, laterally by the sternocleidomastoid muscles, and inferiorly by the hyoid bone. The subjects and evaluating investigator will be blinded to the treatment, thus maintaining double-blind status. By nature of the varying volumes of injection, the treating investigator will be unblinded to the treatment. A series of 3 injection sessions will be performed spaced 4 weeks apart. No lidocaine will be injected prior to injections to prevent further dilution of injected KybellaTM as it will be

premixed with KybellaTM. Chilling with cold will be the method of pain reduction for needle insertion.

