Canfield Vectra 3D imaging will be performed at baseline and final visit (Appendix C) with analysis and calculation of volumetric changes performed at baseline and final visit. Photos will also be taken with the Intellistudio at all other visits. Follow up visits will be performed 3 and 5 days after each injection session to assess for side effect and tolerability profile. After the final injection session, additional follow up visits will be performed at days 90 and 180 to assess for efficacy. Subject weight will be recorded at baseline and at end of study.

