# 4.3 INCLUSION CRITERIA

The following are requirements for a potential subject's inclusion into the study:

- 1. Females or Males in good general health age 18 65 years of age
- 2. Fitzpatrick skin types I-VI
- 3. Must be willing to give and sign a HIPAA form and informed consent form
- 4. Must be willing and able to comply with all study protocols and schedules
- 5. Must have submental fat graded by the investigator as 2 or 3 using the Clinician-Reported Submental Fat Rating Scale (PR-SMFRS)
- 6. Negative urine pregnancy test prior to each treatment (if applicable)

- 7. Female patients will be either of **non-childbearing potential** defined as:
  - 7.1 Having no uterus
  - 7.2 No menses for at least 12 months.

Or:

**(WOCBP)** women of childbearing potential must agree to use an effective method of birth control during the course of the study, such as:

- 7.3 Oral contraceptive pill, injection, implant, patch, vaginal ring, intrauterine device
- 7.4 Intrauterine coil
- 7.5 Bilateral tubal ligation
- 7.6 Barrier method used with an additional form of contraception (e.g., sponge, spermicide or condom)
- 7.7 Abstinence (If practicing abstinence must agree to use barrier method described above (7.6) if becomes sexually active)
- 7.8 Vasectomized partner (must agree to use barrier method described above (7.6) if becomes sexually active with unvasectomized partner)
- 8. Males must be willing to be clean shaven for all study visits
- 9. The patient must have had a stable weight (no fluctuation of >15 pounds in a year), diet, and physical activity for the previous 6 months

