# B. Subject Discontinuation

**Each subject may voluntarily discontinue** the study at any time they choose. Subjects who cannot complete the study for administrative reasons (e.g., non-compliance, failure to meet visit schedule, etc.) will be discontinued from the study. These patients will be asked to return for completion of visit 11.

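### The hypothesis that triamcinolone preserves fat reduction has no criterion that could support it: the only rule is p ≤ 0.05, and a non-significant result from 10 versus 20 subjects does not show preserved efficacy

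*Combined protocol and SAP*

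**What the plan says.** Section 2 gives the working hypothesis two main parts: TMC reduces immediate edema, and it "does not adversely affect the previously demonstrated long term reduction of submental fat". The second part matters because Section 1 reports that TMC in an earlier randomised study "reduced the incidence of early edema and tenderness, but negatively impacted long term efficacy".

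Section 3 sets the size: "30 subjects will be enrolled into the trial (15 subjects per site"), with 5 control and 10 TMC subjects at each site. It also says that "additional follow up visits will be performed at days 90 and 180 to assess for efficacy", and that Vectra imaging will be used with "analysis and calculation of volumetric changes performed at baseline and final visit". Eligibility (Section 4.3) limits baseline severity: "Must have submental fat graded by the investigator as 2 or 3 using the Clinician-Reported Submental Fat Rating Scale".

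Section 14 lists rating scales and visits and ends with its one inferential statement: "A p value of 0.05 or less will be considered significant". Neither Section 14 nor any other section gives a test, an efficacy estimate, a CI, a margin, an analysis set, a missing-data method or a sample-size rationale.

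Section 6.4 B says of discontinued subjects: "These patients will be asked to return for completion of visit 11". Section 6.4 C covers subjects terminated for moderate to severe irritation or a severe adverse event. It counts them as completers, does not replace them, and does not say whether they are asked back for Visit 11.

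**The concern.** A significance threshold answers whether the arms differ. The hypothesis asks whether TMC is no worse than control by more than an acceptable amount. Under the rule as written, the only result that could be offered in support is p above 0.05, and a smaller or noisier trial makes that result more likely. A report could then present a lack of evidence of harm as evidence of no harm, on the very outcome that the protocol says suffered in the earlier TMC study.

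The analysis set adds to the problem. Subjects who stop treatment early may have different fat reduction, and the plan does not say whether or how their Day 180 grades enter the comparison.

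**Working it through.** **Inputs from the protocol.** Control 2 × 5 = 10; TMC 2 × 10 = 20; total 30, which agrees with Section 3. Alpha is 0.05 (Section 14); sidedness is not stated and is taken as two-sided. The plan derives no sample size, so there is no power figure to reproduce.

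**Assumptions.** SD of CR-SMFRS change of 0.5, 0.6, 0.8 or 1.0 grade; true losses of half a grade or one grade; all 30 subjects analysed. The documents give none of these values. For scale, baseline is grade 2 or 3, so the largest possible reduction is 2 to 3 grades. Half a grade is 0.5/3 to 0.5/2, or 17–25% of that; one grade is 33–50%.

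**Precision.** Half-width = t(0.975, 28) × SD × √(1/10 + 1/20) = 2.048 × 0.387 × SD = 0.793 SD. After adjustment for baseline grade and site (26 df) it is 0.796 residual SD.

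**Chance of missing a true loss.** The two-sided t-test was evaluated with the non-central t distribution on 28 df, with non-centrality = loss / (0.387 × SD). For a half-grade loss this is 2.58, 2.15, 1.61 and 1.29 at the four SDs.

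**Power against a margin.** This is the chance that the two-sided 95% CI excludes a loss of the stated size when there is no true difference.

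| Assumed SD (grade) | 0.5 | 0.6 | 0.8 | 1.0 |
|---|---|---|---|---|
| CI half-width (grade) | 0.40 | 0.48 | 0.63 | 0.79 |
| Half-grade loss non-significant | 30% | 45% | 66% | 76% |
| One-grade loss non-significant | 0.1% | 1% | 12% | 30% |
| Power, half-grade margin | 70% | 55% | 34% | 24% |
| Power, one-grade margin | >99% | 99% | 88% | 70% |

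80% power needs a margin of 1.12 SD, that is 0.56, 0.67, 0.90 or 1.12 grade.

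**Whole-grade scoring.** The scale is ordinal, so mean-based figures are approximate. In a simulation with change rounded to whole grades (40,000 runs), realised SDs of 0.57, 0.66, 0.85 and 1.01 gave non-significance for a half-grade loss 42%, 53%, 69% and 77% of the time, in line with the formula.

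**Why no-change imputation is unsafe.** Suppose 3 of 10 controls and 2 of 20 TMC subjects are terminated, control subjects otherwise improve by 1 grade, and TMC truly costs 0.5 grade (all assumed). Setting terminated subjects to no change gives control 0.7 × 1.0 = 0.70 and TMC 0.9 × 0.5 = 0.45. The apparent loss is 0.25 grade, half the true one.

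**The case against.** Four points can be made on the other side.

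- **The misuse is not written down.** A reader might infer that the plan will treat p above 0.05 as proof of preserved efficacy. No section says so; Section 14 names no test at all. This stands: the defect is a missing criterion, and the misreading is a risk that the gap leaves open.
- **The trial is not blind to every loss.** A reader might infer that 30 subjects can show nothing about efficacy. The figures do not support that. If only a full-grade loss mattered and the SD were 0.8 or less, the trial would detect it, or exclude it when there is no true difference, about 88% of the time or more. Even then a margin and CI rule stated in advance would be needed.
- **The time point is less open than it looks.** Section 3 names both Day 90 and Day 180 for efficacy. The long-term wording of the hypothesis, final-visit Vectra imaging and Day 180 satisfaction all point to Day 180. This stands, and makes the choice easy to write down.
- **The direction of any termination bias is unknown.** A reader might infer that irritation would remove more controls and so hide a TMC loss. Section 6.4 C also covers severe adverse events, and Section 1 reports steroid atrophy in 7 of 15 TMC-treated patients, so terminations could fall more on either arm. The documents support planning for both directions, not predicting one.

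A reader might also set aside the earlier loss of efficacy as an effect of a much higher TMC dose. The protocol's mixing figures do not bear that out: 0.05 mL × 40 mg/mL (Section 1) and 0.2 mL × 10 mg/mL (Section 3) are both 2 mg TMC per 2.0 mL of Kybella. Those passages and the dose descriptions need to be reconciled; this point does not depend on the outcome.

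**Conclusion.** The concern holds, and should be fixed before analysis. The plan states a no-worse-than hypothesis and supplies only a rule for detecting differences. That mismatch does not depend on any assumed number, because non-significance is not evidence of preserved efficacy at any sample size.

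How much it matters here does depend on assumptions. Across SDs of 0.5 to 1.0 grade, a half-grade loss would go undetected in 30% to 76% of such trials, while a one-grade loss would usually be detected unless the SD is near 1.0, where it is missed 30% of the time. Whether half a grade is clinically important is for the sponsor to justify; the documents do not say. Missing Day 180 grades would reduce precision further and could bias the comparison in either direction.

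**What to change.** In Section 14:

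1. Name the efficacy estimate: the TMC minus control difference in CR-SMFRS change from baseline to Day 180 (positive means a loss with TMC), adjusted for baseline grade and site, with a two-sided 95% CI.
2. Analyse all randomised subjects in their assigned arm. Use every Day 180 grade obtained, including those from discontinued subjects who return under Section 6.4 B, and state how missing grades are handled. Reconcile Sections 6.4 B and 6.4 C on whether terminated subjects are also asked to attend Visit 11.
3. Conclude that efficacy is preserved only if the CI excludes a loss larger than a margin that the sponsor justifies in advance. If no margin can be justified, label the comparison estimation only and report the estimate and CI. In neither case read p above 0.05 as preserved efficacy.
4. In any sensitivity analysis for missing grades, vary the assumed outcome separately in each arm, including values favourable to terminated controls and unfavourable to terminated TMC subjects. Do not rely on no-change imputation.
5. Report Vectra volume change the same way, as supporting evidence.

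**Cost.** Text changes in Section 14, with matching wording in Sections 2, 4.2 and 6.4. No new scheduled visits or larger sample are required; if the reconciliation asks terminated subjects back, those individuals attend the existing Visit 11. The sponsor must justify a margin or accept the estimation-only label. The downside is a possibly inconclusive efficacy result: with no true difference, power at a half-grade margin runs from 70% down to 24% over the assumed SDs.

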# 4.2 Study Endpoints

# a. Investigator Evaluations (Appendix A)

- The Clinician-Reported Submental Fat Rating Scale will be completed by a blinded-investigator on Visit Days 1, 30, 60, 90 and 180.
- The Submental Skin Laxity Grade (SMSLG) will be completed by a blinded-investigator on Visit Days 1, 30, 60, 90, and 180.
- A Side Effects Scale will be completed by a blinded-investigator at all follow-up visits. The side effects evaluated will include Edema, Erythema, Tenderness, Erosion/Ulceration, Steroid Atrophy, Induration, and Marginal Mandibular Palsy.

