# b. Subject Evaluations (Appendix B)

- The Subject Evaluation of Side Effects Scale will be completed at Visits 2 through 11.
- The Subject Satisfaction Rating Scale will be completed by the patient on Visit Day 180.

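### Section 14 sets an unadjusted p ≤ 0.05 with no decisive edema or pain measure: over 24 acute comparisons, an inert additive would produce a result favouring triamcinolone in about 10–32% of trials, depending on an assumed correlation

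*Combined protocol and SAP*

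**What the plan says.** Section 14 (Data Analysis) lists who rates what and when, and ends with its only inferential statement: "A p value of 0.05 or less will be considered significant". It gives no test, sidedness, summary over visits, primary endpoint, primary time point or multiplicity rule.

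The rest of the document does not fill the gap. Section 2 joins three outcomes in one objective: "The primary objective of this study is to evaluate the efficacy, edema and pain associated with Kybella(TM) injections". Section 4.2 lists scales without ranking them: "A Side Effects Scale will be completed by a blinded-investigator at all follow-up visits", and "The Subject Evaluation of Side Effects Scale will be completed at Visits 2 through 11".

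Section 14 has three sets of side-effect ratings:
- The blinded clinician grades "erythema, edema, tenderness, and erosion/ulceration at each follow-up visit".
- "The subject will evaluate the side effects of bruising, pain, swelling, tolerability, and interference in daily function on a scale of 0-4", at every follow-up visit.
- "The investigator will also evaluate the side effects of bruising, pain, swelling, tolerability, and interference in daily function", again at every follow-up visit.

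Two other statements bear on the point. The working hypothesis in Section 2 credits TMC with reducing immediate edema without loss of fat reduction, and credits lidocaine with immediate pain relief. Section 3 gives both groups the same 0.2 mL of 1% lidocaine, and sets visits 3 and 5 days after each session to look at side effects and tolerability.

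**The concern.** Edema is recorded as clinician edema, subject swelling and a further investigator swelling rating. Pain is recorded as subject pain, clinician tenderness and a further investigator pain rating. Each is repeated over 10 follow-up visits, and nothing says which combination of item, rater and visit decides the edema or the pain question.

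The choice can therefore be made after the data are seen. A single favourable cell could be presented as support for the hypothesis, and a reader could not tell it from a result fixed in advance. The error rate of the edema and pain conclusions would not be the 5% that the sentence suggests. With 30 subjects and no stated sample-size rationale, an isolated small p value is weak evidence to begin with.

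**Working it through.** The plan states no family-wise error rate, power or effect size, so there is no figure of its own to reproduce.

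**Inputs from the document**
- Threshold 0.05 (Section 14), taken as two-sided because sidedness is not stated.
- Arms of 10 and 20 (Section 3: 5 and 10 at each of two sites; 2×5 + 2×10 = 30).
- Ten follow-up visits, 2 to 11 (Sections 4.2 and 6).
- Six acute visits: 2, 3, 5, 6, 8 and 9 (Sections 3 and 6).

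**What the text permits.** In Section 14: 4 clinician items × 10 + 5 subject items × 10 + 5 investigator items × 10 + 4 post-baseline fat ratings + 1 satisfaction rating = 145. Section 4.2 and the appendices, without the five extra investigator items, give 7×10 + 5×10 + 4 fat + 4 laxity + 1 = 129.

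**The narrower family.** Clinician edema, clinician tenderness, subject swelling and subject pain at six acute visits: 4 × 6 = 24.

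**Upper reference, independent tests**
- Either direction: 1 − 0.95^24 = 70.8%.
- Favouring TMC: 1 − 0.975^24 = 45.5%.

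**Correlated ratings.** Ratings on the same subject are correlated, but the documents do not say how strongly, so a range is needed. The chance of at least one p ≤ 0.05 among the 24 with no true effect was found in three ways:
- A: simulated 0–4 grades, 10 vs 20 subjects, equal correlation between all ratings, rank test.
- B: 24 equally correlated z-statistics.
- C: simulated 0–4 grades with separate item and visit correlations, both set to the value shown.

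Entries are either direction / favouring TMC.

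| Assumed correlation | A | B | C |
|---|---|---|---|
| 0.3 | 60% / 32% | 60% / 32% | 64% / 37% |
| 0.5 | 47% / 24% | 45% / 22% | 55% / 29% |
| 0.7 | 37% / 19% | 31% / 15% | 41% / 22% |
| 0.9 | 20% / 10% | 17% / 8% | 26% / 12% |

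Repeat runs of A moved its figures by at most 3 percentage points. A is used for the headline range. Against one test:
- Favouring TMC: 10/2.5 = 4 times to 32/2.5 = 12.8 times.
- Either direction: 20/5 = 4 times to 60/5 = 12 times.

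**With a rule in place.** One edema test and one pain test, each at 0.05 with either allowed to win, give up to 1 − 0.95² = 9.75% under independence. If pain is tested only after edema succeeds, the chance of any false claim from the pair is at most 5%.

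**Precision of a six-visit mean.** Relative to a single visit, its standard error is √((1+5r)/6): 0.65, 0.76 and 0.87 at r = 0.3, 0.5 and 0.7, and 0.96 at r = 0.9. The formula assumes complete data, equal variances and equal correlations.

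**The case against.** The best reply is that the plan never commits to testing every item at every visit. That is correct. The figure 145 is a ceiling, and 50 of it come from a sentence giving the investigator the subject's five items, for which Appendix A has no clinician form. Section 2 speaks of immediate edema and Section 3 ties the day 3 and day 5 visits to side effects, so a Day 90 or Day 180 edema cell would not credibly support the hypothesis. This is why the working uses 24 comparisons.

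A reader might infer that the 145 comparisons carry about a one-in-two chance of a false edema or pain finding. The documents do not support that. One in two is roughly the either-direction result for 24 comparisons at an assumed correlation of 0.5 (47%). For 145 the chance is 99.9% under independence and 55% at correlation 0.7.

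A reader might also infer that any significant cell could be offered as confirmation. It could not: the hypothesis is a reduction, so cells favouring Kybella alone count against it. The relevant range is the lower one, and for edema alone (2 items × 6 visits = 12 comparisons) it is about 22%, 16%, 12% and 8% at correlations 0.3, 0.5, 0.7 and 0.9.

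The objection changes the size of the problem but does not remove it. Even one summary test for each of the four edema and pain items gives about 10–17% in either direction at correlations 0.9 to 0.3, and the plan does not commit to that either.

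**Conclusion.** The point holds in this limited form and should be settled before the data are analysed. The stated rule does not control error for the edema or pain claims, and nothing else in the document limits which comparison may be used.

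Over the 24 acute comparisons, an inert additive would give at least one result favouring TMC in about 10–32% of trials, and one in either direction in about 20–60%, against 2.5% and 5% for a single test. No scenario examined for these 24 returns to the nominal level.

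The missing hierarchy is plain from the text. The percentages are less certain: they rest on assumed correlations of 0.9 to 0.3, assumed grade distributions, two-sided tests and every one of the 24 cells being examined.

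**What to change.** Replace the sentence in Section 14 with a fixed sequence at two-sided 5%:

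1. Blinded-clinician edema, as the difference between arms averaged over Visits 2, 3, 5, 6, 8 and 9. Use every available visit, for example in a repeated-measures model, so that subjects terminated under Section 6.4 C stay in the analysis. State the missing-data assumption, because those with marked irritation may lack later acute visits.
2. Only if step 1 is met, subject-rated pain on the same six-visit summary. Label it as the effect of TMC on day 3–5 pain. Both arms receive the same lidocaine and pain is first rated at Visit 2 (Day 3), so this comparison cannot test immediate relief from lidocaine.

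Name the Day 180 difference between arms on the Clinician-Reported Submental Fat Rating Scale as the efficacy result, with a 95% confidence interval. No margin is stated, so a non-significant p must not be read as showing no loss of efficacy. Report all other items, raters and visits as estimates with 95% confidence intervals and no significance claim.

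Edema comes first because it is the effect that Section 2 ascribes to TMC. Choosing the clinician over the subject, and an average over a peak, is a judgement. Another choice would serve if it were fixed before unblinding.

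The cost is a few sentences, with no added visits or subjects. Under the conditions given with the formula, the six-visit mean has a standard error 13–35% below that of a single visit at correlations 0.7 to 0.3, and about 4% below at 0.9. The downside is that single-visit and single-item p values can no longer be claimed as findings.
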